# **4.3.** Description of Treatment

OTX-DP (dexamethasone ophthalmic insert, 0.4mg) is a resorbable hydrogel intracanalicular insert consisting of two main components: dexamethasone and a polyethylene glycol (PEG)- based hydrogel conjugated with fluorescein.

The hydrogel intracanalicular insert is designed to be placed in the canaliculus and swell on contact with moisture to occlude the lumen, securing it in place. Once the OTX-DP or PV swells to fill the canaliculus, it is designed to hydrolyze and be resorbed.

OTX-DP or PV is provided to the Investigator as a terminally-sterilized dried product. The product is packaged in a hermetically sealed foil pouch to maintain stability and sterility over time. It is placed into the punctum (Figure 1) by the Investigator using forceps. The instructions for the insertion procedure are described in Appendix G.

[figure not shown]

Figure 1 Placement of Intracanalicular Insert in the Canaliculus

CLN-Protocol-0052 Rev 002: 29-October 2019

#### 4.3.1. Placebo Vehicle

The control, PV, is the same fluorescent PEG hydrogel as OTX-DP, except that it does not contain drug.

### 4.3.2. Safety of OTX-DP

Additional details as to the physical, chemical and pharmaceutical properties and product description are provided in the Investigator's Brochure (IB). Packaging configuration is also provided in the IB.

### 4.4. Intended Indication

OTX-DP is being studied for the intended use in the treatment of ocular itching associated with allergic conjunctivitis.

### 4.5. Risk/Benefits

The potential risks and benefits associated with the use of the OTX-DP or PV are described below.

#### **4.5.1.** Potential Benefits

The benefits of OTX-DP are not yet known, but are thought to be:

- Reduction of signs and symptoms associated with allergic conjunctivitis.
- Improved treatment outcome through eliminating subject non-compliance with the use of daily drops.
- Improved treatment outcome through the delivery of therapeutic levels of dexamethasone continuously for the intended duration of therapy and the elimination of preservatives commonly found in ophthalmic preparations.

#### 4.5.2. Potential Risks

In general, the following risks could occur from the insertion and use of the OTX-DP or PV:

- Ocular pain and discomfort
- Conjunctivitis
- Blepharitis
- Epiphora
- Ocular pruritus
- Perforation of or trauma to the punctum and/or surrounding tissues; or punctoplasty
- Allergic reaction
- Impaired visual acuity
- Chemosis
- Inflammatory reaction
- Canaliculitis
- Dacrocystitis

CLN-Protocol-0052 Page **19** of **61** 

- Tearing with mucopurulent discharge
- Stenosis (narrowing/closing) of the punctum
- IOP elevation
- Cataract formation
- Increased risk of infection
- Infection that if severe could lead temporary or permanent impairment of sight
- Inability to remove the OTX-DP or PV

## 5. STUDY OBJECTIVES AND DESIGN

This is a prospective, multi-center, randomized, double-masked, vehicle-controlled study to evaluate the efficacy and safety of OTX-DP compared to PV for the treatment of the signs and symptoms of allergic conjunctivitis.

The modified Ora-CAC® model used in the current study has been developed to study the interactions between the early and late phases of the allergic response in the eye, and to evaluate the effects of pharmaceutical intervention. The modified CAC model utilizes 3 challenges conducted over a 2-day interval to evaluate the effectiveness of a test agent to: 1) prevent an acute ocular allergic reaction (the initial CAC), and 2) evaluate the test agent's ability to prevent an acute ocular allergic reaction in the presence of subclinical late phase inflammation (the latter re-challenge CACs).

The modified CAC model provides the opportunity to investigate the effects of the underlying inflammatory reaction on the ability of the tissues to mount a robust acute response to a subsequent allergen challenge. The modified CAC model also provides a means to investigate the mechanism(s) of action of anti-inflammatory agents in the treatment of allergic reactions.

This study will comprise of 13 office visits over a period of approximately 5 to 11 weeks. Visits 2, 3a, 3b, and 4a will be used to select a subject population that responds reproducibly to the 3 CACs administered over a 2-day interval used in the modified Ora-CAC model to induce the underlying inflammatory component characteristic of chronic allergic conjunctivitis. Subjects who meet the entry criteria for itching and redness response to the CAC at Visits 2, 3a, 3b, and 4a will be randomized at a 1:1 ratio (active:vehicle) at Visit 4b (Day 1) to receive one of the following treatment arms bilaterally:

- OTX-DP (N=40 subjects) or
- PV (N=40 subjects)

In the OTX-DP arm, subjects will receive bilateral OTX-DP (dexamethasone ophthalmic insert, 0.4mg) inserts.

The series of CACs and re-challenge CACs during Visits 5, 6a, and 6b will be used for the primary efficacy measures at Visit 6b and will assess the effectiveness of the OTX-DP (beginning at 5 days post-insertion, with the primary endpoint at 7 days post-insertion). Subjects will return to the office for Visits 7, 8a, and 8b for another series of CAC and re-challenge CACs and will return again for Visit 9 (Day 30+3) for the removal of OTX-DP or PV, if still present, and for final safety evaluations.

# 5.1. Study Objectives

To evaluate the efficacy and safety of OTX-DP as a dexamethasone ophthalmic insert when placed in the canaliculus of the eyelid for the treatment of the signs and symptoms of allergic conjunctivitis.

CLN-Protocol-0052 Page **20** of **61** 

# **5.2.** Clinical Hypothesis

Statistical hypotheses for the primary efficacy endpoint of ocular itching at Visit 6b are as follows:

H10: There is no difference in mean ocular itching scores between OTX-DP and PV treated subjects for at least 1 of the 3 time points during Visit 6b.

H1a: There is a difference in mean ocular itching scores between OTX-DP and PV treated subjects for all 3 time points during Visit 6b.

Similar hypotheses will be tested for the key secondary efficacy endpoints of ocular itching at Visits 5, 6a, 7, 8a, 8b. Statistical significance will be determined using a two-sided significance level of 0.05.

# **5.3.** Efficacy and Safety Parameters

### **5.3.1.** Primary Efficacy Evaluations

The primary endpoint is:

• Ocular itching evaluated by the subject on Visit 6b (Day 8; 7 days post-insertion; 8 hours from Visit 6a) at 3(±1), 5(±1), and 7(±1) minutes post-CAC (0-4 scale, allowing half unit increments)

## **5.3.2.** Secondary Efficacy Evaluations

Key secondary outcomes are the measures of ocular itching at the following visits at  $3(\pm 1)$ ,  $5(\pm 1)$ , and  $7(\pm 1)$  minutes post-CAC:

- Visit 6a (Day 8; 7 days post-insertion)
- Visit 5 (Day 7; 6 days post-insertion)
- Visit 8b (Day 15; 14 days post-insertion; 8 hours from Visit 8a)
- Visit 8a (Day 15; 14 days post-insertion)
- Visit 7 (Day 14; 13 days post-insertion)

Other secondary efficacy measures are ocular itching at Visits 5, 6a, 6b, 7, 8a, and 8b at the  $10(\pm 1)$  minutes post-CAC and the following assessments made at Visits 5, 6a, 6b, 7, 8a, and 8b at  $7(\pm 1)$ ,  $15(\pm 1)$ , and  $20(\pm 3)$  minutes post-CAC:

- Conjunctival redness evaluated by the investigator (0-4 scale, allowing half unit increments)
- Ciliary and episcleral redness evaluated by the investigator (0-4 scale, allowing half unit increments)
- Chemosis evaluated by the investigator (0-4 scale, allowing half unit increments)
- Eyelid swelling evaluated by the subject (0-3 scale, NOT allowing half unit increments)
- Tearing/watery eyes evaluated by the subject (0-4 scale, NOT allowing half unit increments)
- Rhinorrhea, nasal pruritus, ear or palate pruritus, and nasal congestion evaluated by the subject (0-4 scale, NOT allowing half-unit increments)

CLN-Protocol-0052 Page **21** of **61** 

• Nasal symptom composite score based on the assessments of rhinorrhea, nasal pruritus, ear or palate pruritus, and nasal congestion (analyzed as a qualitative measure determined as the presence or absence of at least one nasal symptom [present/absent], and as a quantitative measure calculated as the sum of the four component symptom scores [ranging from 0 to 16])

## **5.3.3.** Safety Evaluations

- Adverse Events (AEs) (reported, elicited, and observed)
- Best Corrected Visual Acuity (BCVA) using an ETDRS chart
- Slit-lamp biomicroscopy, including punctum exam
- Intraocular Pressure (IOP)
- Dilated Fundoscopy Examination

# **5.4.** Training of Investigators

Only ophthalmologists or optometrists who are experienced with punctal plug insertion will be considered for participation as Principal Investigators or Sub-Investigators in this study. All investigators who will use the OTX-DP or PV will undergo training on instructions for the insertion procedure which can be found in Appendix G.

# 5.5. Subject Selection

### 5.5.1. Study Population

Subjects of at least 18 years of age of either sex and of any race, who meet all of the inclusion criteria and none of the exclusion criteria.

#### 5.5.2. Inclusion Criteria

Each subject must:

- 1. be at least 18 years of age of either sex and any race;
- 2. provide written informed consent and sign the HIPAA form;
- 3. be willing and able to follow all instructions and attend all study visits;
- 4. be able and willing to avoid all disallowed medication for the appropriate washout period and during the study (see exclusion 6 in Section 5.5.3).
- 5. be able and willing to discontinue wearing contact lenses for at least 72 hours prior to Visit 2 and during the study period;
- 6. have a BCVA of greater than or equal to 50 ETDRS letters (20/100 Snellen equivalent or better) in each eye as measured at Visit 1;
- 7. agree to have urine pregnancy testing (for women considered capable of becoming pregnant, including all females who have experienced menarche and have not experienced menopause [as defined by amenorrhea for greater than 12 consecutive months] or have not undergone successful surgical sterilization [hysterectomy, bilateral tubal ligation, or bilateral oophorectomy]) performed at Visit 2 and at the exit visit; not be lactating; and agree to use a medically acceptable form of birth control throughout the clinical study duration;

CLN-Protocol-0052 Page **22** of **61** 

- 8. have a positive history of ocular allergies and a positive skin test reaction to a perennial allergen (cat dander, dog dander, dust mites, cockroaches) and a seasonal allergen (trees, grasses, and/or ragweed) as confirmed by the allergic skin test conducted at Visit 1 or given to the subject within 24 months of the subject's Visit 2;
- 9. have a positive bilateral CAC reaction (defined as  $\geq 2$  itching and  $\geq 2$  conjunctival redness) within 10 (±2) minutes of instillation of the last titration of allergen at Visit 2;
- 10. have an average of  $\geq$  3 itching and  $\geq$ 2.5 conjunctival redness for both eyes after the first three post-CAC assessment time points at Visit 4a.

#### 5.5.3. **Exclusion Criteria**

Each subject must not:

- 1. have known contraindications or sensitivities to the use of any of the medications required by the protocol;
- 2. have any ocular condition that, in the opinion of the investigator, could affect the subject's safety or study parameters (including but not limited to narrow angle glaucoma, clinically significant blepharitis, follicular conjunctivitis, iritis, pterygium or a diagnosis of dry eye);
- 3. have had a history of refractive surgery (including LASIK procedures) within the past 2 years;
- 4. have a known history of retinal detachment, diabetic retinopathy, or active retinal disease;
- 5. have the presence of an active ocular infection (bacterial, viral or fungal), a current diagnosis or history of Herpes Simplex Keratitis, or a positive history of an ocular herpetic infection at any visit;
- 6. use any of the following disallowed medications\* during the period indicated **prior to Visit 2** and during the study:

#### 7 Days

- systemic or ocular H1 antihistamine, H1 antihistamine/mast-cell stabilizer drug combinations, H1 antihistamine- vasoconstrictor drug combinations;
- decongestants;
- monoamine oxidase inhibitors;
- all other topical ophthalmic preparations (including artificial tears);
- lid scrubs;
- prostaglandins or prostaglandin derivatives;
- ocular, topical, or systemic nonsteroidal anti-inflammatory drugs (NSAIDs);

\*Baby aspirin (81 mg) is allowed as long as a stable dose has been maintained for at least 30 days prior to Visit 2 and will continue to be maintained for the duration of the study.

#### 14 Days

inhaled, ocular or topical corticosteroids or mast cell stabilizers;

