## **45 Days**

depot-corticosteroids;

CLN-Protocol-0052 Page 23 of 61

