### **7.6.** Concomitant Medications

A concomitant medication is any drug or substance administered from Visit 1 (Screening) through the last study visit, Visit 9 (Day 30). The generic name of the drug or substance, the dose, the route of administration, the duration of treatment (including the start and stop dates), the frequency, the indication, and whether or not the medication was taken due to an AE will be recorded for each drug or substance.

Subjects should be instructed not to start taking any new medications, including nonprescription drugs and herbal preparations, unless they have received permission from the Investigator. The use of any concurrent medication, prescription or over-the-counter (OTC), is to be recorded on the subject's

CLN-Protocol-0052 Page **26** of **61** 

Rev 002: 29-October 2019

source document and corresponding eCRF along with the reason the medication was taken.

Concurrent enrollment in another investigational product study is not permitted.

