#### 7.7. **Rescue Therapy**

Cold compress should first be used in the management of allergic symptoms. Subjects may be prescribed anti-inflammatory or anti-allergy medication at the Investigator's discretion. If prescribed such anti-inflammatory or anti-allergy medication, the insert will not be removed and subjects will be followed for safety only.

Currently marketed over-the-counter anti-allergy eye drops (i.e., anti-histamine/ vasoconstrictor combination products such as Visine®-A®) may be administered to subjects at the end of the subject's last visit, after all evaluations are completed.

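### Exclusion 6 does not name systemic corticosteroids, so an existing oral-steroid user who still responds at Visit 4a can enter a corticosteroid trial; the likely cost is modest dilution and some confounding of the IOP data

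*Protocol*

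**What the plan says.** Exclusion 6 (Protocol Section 5.5.3) bars subjects who "use any of the following disallowed medications" for stated periods before Visit 2 and while on study. The entries that matter here are:

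- 7 days: "systemic or ocular H1 antihistamine", and among anti-inflammatories "ocular, topical, or systemic nonsteroidal anti-inflammatory drugs (NSAIDs". Both name the systemic route.
- 14 days: "inhaled, ocular or topical corticosteroids or mast cell stabilizers".
- 45 days: "depot-corticosteroids".

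The synopsis gives the same corticosteroid routes. Neither copy mentions oral or other systemic non-depot corticosteroids.

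Inclusion 4 requires subjects to "be able and willing to avoid all disallowed medication for the appropriate washout period and during the study", and it refers back to exclusion 6 for the list. Section 7.6 deals with new drugs: "Subjects should be instructed not to start taking any new medications" unless the investigator allows it. Section 7.7, on management of allergic symptoms, says: "If prescribed such anti-inflammatory or anti-allergy medication, the insert will not be removed and subjects will be followed for safety only". The SAP adds no medication restriction of its own.

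**The concern.** The list works by route, and its authors wrote the systemic route where they wanted it. Applied as written, a site must turn away a subject on an inhaled steroid or an oral NSAID but may enrol one on an oral corticosteroid. The protocol gives no reason for that ordering.

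It matters because the test drug belongs to the class left open. Protocol Section 4.2 says glucocorticoids reduce allergic signs and symptoms in the acute time frame as well as later, and the 3-, 5- and 7-minute itching scores measure that acute response. Background systemic steroid gives both arms exposure to the same class, which can shrink the difference the insert is meant to show. A course tapered or stopped between Visit 4a and Visit 6b would also make the Visit 4a score a weaker covariate. Section 4.2 further lists glaucoma among glucocorticoid side effects and raised pressure as a concern with local use, so extra steroid exposure blurs the attribution of any IOP rise. Since the use breaks no rule, no planned analysis sets it aside.

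**Working it through.** **1. Does any other provision close the gap?**

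- Inclusion 4 only points back to exclusion 6, so it adds no drug.
- Section 7.6 limits new starts. It does not stop a drug already in use.
- Section 7.7 concerns medication prescribed for allergic symptoms. It does not reach a steroid taken for another condition before entry.
- Exclusion 8 removes only uncontrolled illness. Exclusion 16 removes only subjects with a past IOP rise on steroids, not current users.
- The immunotherapeutic-agents entry of exclusion 6 permits stable use, so it cannot serve as a ban.
- The worst-case imputation in SAP Section 8.2.1 acts only on scores that are missing because of prescribed rescue. A user with recorded scores is untouched.
- Per-protocol exclusion (Protocol Section 10.1.2, SAP Section 7.2) needs a major violation, and permitted use is not one.

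None of these closes it.

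**2. The plan's power figures.** Inputs from Protocol Section 10.6 and SAP Section 5: 40 per arm, SD 1.0, two-sided 5% level, differences of 0.87, 1.08 and 1.13 at 3, 5 and 7 minutes. For a two-sample t-test with 78 degrees of freedom, the noncentrality is d / (SD × √(2/40)) = d / 0.2236, that is 3.89, 4.83 and 5.05. Power is 97.0%, 99.8% and 99.9%. The product, using the plan's independence assumption, is 0.9701 × 0.9975 × 0.9988 = 96.7%. All four stated figures reproduce.

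**3. Effect of users under an assumption.** The documents give no share of oral-steroid users. Let a fraction f in each arm be users, and suppose they gain nothing from the insert. Each difference becomes d × (1 − f), with the SD unchanged.

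| f (assumed) | Differences at 3, 5, 7 min | Power at 3, 5, 7 min | Joint power |
|---|---|---|---|
| 0 | 0.87, 1.08, 1.13 | 97.0%, 99.8%, 99.9% | 96.7% |
| 2.5% | 0.848, 1.053, 1.102 | 96.3%, 99.6%, 99.8% | 95.8% |
| 5% | 0.827, 1.026, 1.074 | 95.5%, 99.5%, 99.7% | 94.7% |
| 10% | 0.783, 0.972, 1.017 | 93.3%, 99.0%, 99.4% | 91.9% |

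If users lost only half of the insert's effect, each row would behave like one with half the fraction. For example, 10% users losing half gives d × 0.95, the 5% row.

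**The case against.** The strongest reply is the entry gate. Inclusion 10 demands average itching of at least 3 and redness of at least 2.5 at Visit 4a. Someone whose oral steroid suppresses the challenge response fails and is not randomised. A stable user who passes has shown near-maximal itching while on the drug, so assuming that the insert adds nothing for that person is severe. This stands, and it makes the table above a pessimistic illustration.

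A reader might infer that the trial could be biased by users falling unevenly between arms. The documents do not support that. Assignment is randomised, and chance imbalance is what the standard error already covers. With four users split 3:1 and each score shifted by a full unit, the difference in means moves by 2/40 = 0.05, against a standard error of 0.22. Likewise, a weaker Visit 4a covariate costs precision, not validity, and unadjusted tests are already planned (Protocol Section 10.8).

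A reader might also infer that subjects may take oral steroid freely during the study. They may not: a new start needs the investigator's permission, and anti-inflammatory medication prescribed for allergic symptoms moves the subject to safety-only follow-up. The gap concerns steroid already in use at entry.

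On IOP, exclusions 15 and 16 remove subjects with high pressure, glaucoma or a past steroid response. Safety data are not formally tested (SAP Section 13), and each concomitant drug is recorded and listed, so users can be identified. The confounding is therefore limited and visible, but it remains.

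Finally, the synopsis and Section 5.5.3 agree with each other on corticosteroids, so the two copies do not conflict. The inconsistency is between entries of one list. That limits the remedy to wording and to a statement of intent.

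**Conclusion.** The omission is certain on the text, and no other provision repairs it. Read literally, an existing oral-corticosteroid user who still reaches the Visit 4a threshold is eligible, may continue, and stays in the per-protocol set.

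The consequence is modest: dilution and noise in the efficacy comparison and some confounding of IOP. There is no systematic bias and no inflation of the type I error. The size rests on an assumed share of users, equal between arms, with no benefit from the insert, unchanged SD and the plan's own independence assumption. Across 2.5% to 10% users, the loss of joint power is about 1 to 5 percentage points (96.7% to between 95.8% and 91.9%). The point is worth correcting because the correction is cheap, not because the trial is endangered.

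**What to change.** Reconcile the corticosteroid entries of exclusion 6 with the antihistamine and NSAID entries, in both the synopsis and Section 5.5.3, so that the list expressly covers the systemic route. Any period is for the sponsor to set; none is proposed here, and nothing in this point calls for a prescribed treatment to be stopped. If the omission is deliberate, the protocol should say so and give the reason.

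With the entry reconciled, class systemic corticosteroid use by a randomised subject as a protocol deviation and assess it for the per-protocol set before database lock and unmasking, as SAP Section 7.2 already provides for deviations in general.

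The cost is one line in an amendment. A few candidates become ineligible. No new data are needed: Section 8.1 already records medications taken or discontinued within the 60 days before Visit 2, and Section 7.6 records concomitant use from Visit 1 to Visit 9.

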## **45 Days**

depot-corticosteroids;

CLN-Protocol-0052 Page 23 of 61

#### 2 Months

- immunotherapeutic agents (treatment must have been maintained steadily for at least 2 months; neither the immunotherapeutic agent nor its dosage may change during the clinical study)
- 7. have a congenital or ocular anomaly (including punctal or lid ectropion, entropion, trichiasis, or supernumerary puncta) or anomalies of the punctum (including lack of good punctal apposition in both eyes);
- 8. have a diagnosis of any significant uncontrolled illness;
- 9. history of alcohol or drug abuse in the past year;
- 10. known history of moderate to severe allergic asthmatic reactions to any of the study allergens;
- 11. have planned surgery (ocular or systemic) during the trial period or within 30 days after;
- 12. have used an investigational drug or medical device within 30 days of the study or be concurrently enrolled in another investigational product trial;
- 13. be a female who is currently pregnant, planning a pregnancy, or lactating;
- 14. have a score of >0 for ocular itching and/or >1 for conjunctival redness prior to the challenge in either eye at Visit 2;
- 15. have an intraocular pressure that is less than 5 mmHg or greater than 22 mmHg or any type of glaucoma at Visit 2;
- 16. have had a history of an IOP increase as a result of steroid treatment;
- 17. have an unsuccessful transient punctum dilation to 0.7 mm prior to insertion of OTX-DP or PV;
- 18. be an employee of the site that is directly involved in the management, administration, or support of the study, or are an immediate family member of the same.

CLN-Protocol-0052 Page **24** of **61** 

